**Table 9 Vital Signs Toxicity Grading Scales**

	Systolic Blood Pressure (mmHg)	Diastolic Blood Pressure (mmHg)
Normal	≤ 140	≤ 90
Grade 1	141-150	91-95
Grade 2	151-155	96-100
Grade 3	> 155	> 100

## 7 CHANGES TO PLANNED ANALYSES

### 7.1 Summary of changes from protocol in this SAP (changes not introduced SAP Part 1 or SAP Part 2)

Changes and clarifications to planned analyses described in the protocol and not already introduced within SAP Part 1 or SAP Part 2 are described in the below table.

Protocol Section	Analysis method described originally in the protocol	Planned Analysis	Reasons for changes
Section 3.1.1 Phase 1/2/3a Substudy Primary Objectives and Endpoints	Safety data from participants in Phase 2/3a will be pooled for all time points and will be displayed separately to safety data from Phase 1.	Safety analyses will mostly be performed on the Phase 1/2/3a populations and we will not be repeated separately for Ph1 and Ph2/3a as described in Table 8 of this SAP	Safety data are comprehensive, with same inclusion and exclusion criteria across Phase 1/2/3a, so not relevant to display safety from a smaller phase 1 set separately
Section 3.1.2 Phase 1/2/3a Substudy Secondary Objectives and Endpoints	Immunogenicity will be at the following time points. - Phase 1 IAS: Day 1 (baseline), Day 29, Day 57, Day 92, Day 394. - Phase 2/3a IAS: Day 1 (baseline), Day 29, Day 57, Day 92, Day 120, Day 394 - Phase 1/2/3a IAS: Day 1 (baseline), Day 29, Day 57, Day 92	Samples were collected at Day 394 but were not analyzed so no Day 394 results will be presented for immunogenicity	Immunogenicity would be affected by recommended routine covid-19 vaccinations as such the immunogenicity results will not represent the persistence after the primary vaccination
		Immunogenicity analyses will mostly be performed on the Phase 1/2/3a populations and we will not be repeated separately for Ph1 and Ph2/3a unless the data is only available for Ph1, Ph1/2 or Ph2/3a as described in Table 7 of this SAP	Immunogenicity data are comprehensive, with same inclusion and exclusion criteria across Phase 1/2/3a, so not relevant to display immunogenicity separately from small phase 1 dataset
Section 3.1.3 Phase 1/2/3a Substudy Exploratory Objectives and Endpoints	To compare the humoral immune responses to ARCT-154 with those following COVID-19	This objective will not be assessed	No convalescent sera results available

Section 3.1.3 Phase 1/2/3a Substudy Exploratory Objectives and Endpoints	Blood samples from post-vaccination timepoints evaluated for immune responses to SARS-CoV-2 VOC/VOI using the following assays PRNT50, sVNT, MNT	PRNT 50 is removed from the exploratory endpoint description	It is already covered in secondary objective 2.
Section 3.3.1 Phase 3c Primary objective	To evaluate noninferiority of neutralizing antibody geometric mean concentration for ARCT-154 versus ChAdOx1 at Day 57	No immunogenicity analysis will be performed for Phase 3c.	Phase 3c samples were not analyzed as this immunogenicity objective is considered not relevant. Clinical efficacy was demonstrated in the phase 3b of this study as such demonstration of immunological comparability against authorized comparator (ChAdOx1) is not required.
Section 3.3.2 Phase 3c Secondary Objectives	Secondary Objectives 1-6 to analyze immunogenicity	No immunogenicity analysis will be performed for Phase 3c.	
Section 3.3.3 Phase 3c Exploratory Objectives	Exploratory Objectives 5-6 to analyze immunogenicity	No immunogenicity analysis will be performed for Phase 3c.	
Section 3.3.3 Phase 3c Exploratory Objectives	Exploratory Objectives 1-4 to analyze efficacy	No efficacy analysis will be performed for Phase 3c.	Covid cases were not adjudicated for this exploratory objective. The clinical exploratory objective is considered not relevant.
Section 8.2 Analysis set  Immunogenicity Analysis Set (IAS)	Phase 1/2/3a IAS this pools data from Phase 1, 2 and 3a participants and will include evaluations of immunogenicity up to Day 92 only.	Phase 1/2/3a IAS (or phase 1/2 IAS): this pools data from Phase 1, 2 and 3a participants and will include evaluations of immunogenicity up to Day 92 only. Of note, this analysis set may be restricted to Phase 1 and Phase 2 participants for analysis on parameter not collected for phase 3a participants.  Phase 1/2/3a PP immunogenicity set (or Phase 1/2 PP	This was done due to some immunogenicity data being collected only for Phase 1 and 2 participants and therefore Phase 1/2/3a PP set is not applicable for such analyses.

	Phase 1/2/3a PP Immunogenicity set: this pools data from Phase 1, 2 and 3a participants and will include evaluations of immunogenicity up to Day 92 only.	immunogenicity set): this pools data from Phase 1, 2 and Phase 3a participants and excludes any participant that has evidence of SARS-CoV-2 infection at baseline or prior to the analysis time point concerned (IcEv3) or that receives a non-study COVID-19 vaccine prior to the analysis time point concerned (IcEv2). This set will include evaluations of immunogenicity up to Day 92 only. Of note, this analysis set will be restricted to Phase 1/2 participants for analysis on parameter not collected for phase 3a participants and will be referred as Phase 1/2 PP immunogenicity set)	
Section 8.2 Analysis Set Immunogenicity (IAS) Analysis set	Includes all participants who received all protocol-required doses of study vaccine (ARCT-154 or placebo or ChAdOx1) up to the evaluation timepoint concerned, who have no evidence of prior SARS-CoV-2 infection at Day 1 (IcEv3; Section 8.3.1) and who have at least 1 valid post-vaccination immunogenicity assay result.	Includes all participants who received all protocol-required doses of study vaccine (ARCT-154 or placebo) up to the evaluation timepoint concerned, who have no evidence of prior SARS-CoV-2 infection (no positive RT-PCR or other COVID-19 test or seropositivity for anti-nucleocapsid antibody) up to Day 57 and who have at least 1 valid post-vaccination immunogenicity assay result.	The definition was updated to clarify that participants with early COVID-19 infection (positive RT-PCR or other COVID-19 test or seropositivity for anti-nucleocapsid antibody) up to Day 57 are excluded from these analysis sets as also described in Tables 14 and 15 of the protocol.
Section 8.2 Analysis set	All participants in the IAS will be analyzed according to which study vaccine was received.	All participants in the IAS will be analyzed according to which study vaccine was assigned.	Align with ICH E9. As per definition of IAS, participants included are those who received the per protocol required dose. Thus in case of midsoring, the participants will be excluded from the IAS.
Section 8.3.1 Table 14 Intercurrent Event types	IcEv3 (Early infection): Positive RT-PCR test or seropositivity for	IcEv3 (Early infection): Positive RT-PCR test or	Addition of other COVID-19 positive test for complete

	antinucleocapsid antibody or neutralizing antibody (as assessed by sVNT for Phase 1/2/3a and MNT for Phase 3c) indicating exposure to SARS-CoV-2 prior to vaccination or SARS-CoV-2 infection prior to 7 days (inclusive) after the second study vaccination dose (Day 35).	other COVID-19 positive test or seropositivity for anti-nucleocapsid antibody indicating exposure to SARS-CoV-2 prior to vaccination or SARS-CoV-2 infection prior to 7 days (inclusive) after the second study vaccination dose (Day 35).  Note: This also impacts mITT and IAS analysis sets definitions where IcEv3 is considered.	assessment of early infection
Section 8.3.1 Table 15 (estimand 1 – Rationale for Strategies)	IcEv4 and IcEv5 could also be potentially confounding but it is more difficult to determine the precise timing of these events, so a principal stratum strategy is used to exclude these participants from immunogenicity analyses.	IcEv4 and IcEv3 could also be potentially confounding but it is more difficult to determine the precise timing of these events, so a principal stratum strategy is used to exclude these participants from immunogenicity analyses.	Correction
Section 8.3.1 Table 17 (estimand 3 – unsolicited Aes - Intercurrent Event (IcEv) Strategy)	Intercurrent Event (IcEv) Strategy:  IcEv2 (Non-study vaccine): treatment policy strategy  IcEv5 (Confounding On-study Medications): composite strategy	IcEv2 (Non-study vaccine): while on treatment strategy  IcEv5 (Confounding On-study Medications): treatment policy strategy	IcEv2: Correction of the name of the strategy to reflect the fact that events occurring after IcEv2 will not be included in the analysis as specified in protocol  IcEv5: Correction of the name of the strategy to reflect the fact that events occurring after IcEv5 are included in the analysis as specified in the protocol
Section 8.3.1 Table 17 (estimand 4 – Reactogenicity - Rationale for Strategies)	Events occurring after IcEv2, IcEv3 and IcEv5 could contribute spurious reactogenicity data so a treatment policy is used for these events and events occurring after	All solicited events will be analyzed regardless of occurrence of intercurrent events.	Reactogenicity is participant reported outcome, which will be analyzed as it is without modification.

	these IcEv's will be summarized separately		
Section 8.7.2 Table 18 estimand 2 (efficacy)	Imputation/Data/Censoring Rules: For deaths unrelated to COVID-19, censor at date of death. For participants who undergo Switchover/Further Study Vaccine or receive a non-study COVID-19 vaccine, censor at date of Switchover or non-study vaccination.	Participants last date at risk date will also be censored for Lost to Follow-up	Add rule of handing censoring condition for lost to follow-up scenario.
Section 8.7.2 Table 18 estimand 2 (efficacy)	Sensitivity: the same analysis will be performed in the Pooled mITT and Phase 3b PP analysis sets.	
2 additional sensitivity analyses to be performed.
 
 
• A sensitivity analysis of all Covid cases reported in CRF and not confirmed by the blinded Independent Adjudication Committee or with severity as reported in the CRF has been added for the primary endpoint, severe cases and deaths due to COVID-19.
 
• Day 36 is defined as second dose+7 days (29+7=36 days), and Day 92 is defined as second dose+63 days (29+63=92 days). Another sensitivity analysis of the primary endpoint (Phase 3b only) will be performed using Day 92 visit instead of second dose+63 days.
 
	Add additional sensitivity analyses to assess the robustness of the primary analysis results.
Section 8.7.2 Table 18 estimand 3 (safety)	Supportive: Analysis will be performed for different time intervals, specifically:	As per section 6.6.1.3 of this SAP, only the following intervals will be done:	To summarize study periods that are not overlapping

	
All MAAEs, AE/SAEs, AEs leading to discontinuation/ withdrawal up to Day 29, Day 57, Day 92, and Day 394 or Final Visit/Early Termination Visit/receipt of non-study COVID-19 vaccine after the first vaccination will be summarized accordingly.
 
AEs occurring after the Day 92 will be recorded and summarized for the interval Day 92 up to Day 394 (Phase 1/2/3a and Phase 3b only). For Phase 1/2/3a and 3b, AEs in participants that do not receive additional study vaccine at Day 92 will be recorded separately for the interval from Day 92 up to Day 394.
	
 
From Day 1 to Day 92 (for participants without Switchover/Further study vaccine) or Switchover/Further study vaccine
 
From Switchover/Further study vaccine to End of Study, for participants with Switchover/Further study vaccine
 
From Day 92 to End of Study, for participants without Switchover/Further study vaccine
 
From the first dose of ARCT-154 vaccine administration to End of Study
 
	
Section 8.7.3.1 Main Estimation of Primary Immunogenicity Endpoint for Phase 1/2/3a Substudy (Estimand 1)	For SCR, chi-square or Fisher's exact test will be used to perform comparison of the two treatment arms. 95% CI of the SCR will also be presented. Pearson's Chi-square test will be used except for the case of small cell count (less than 5).	The number and proportion of participants achieving seroconversion at Day 57 will be provided for each treatment. In addition, the treatment difference in proportion of participants achieving seroconversion at Day 57 will be provided, along with corresponding 95% CI.	No p-value will be computed as the main interest for this analysis is change from baseline.
Section 8.6 Description of Additional Subgroups to Be Analyzed	For immunogenicity subgroup analyses, the following subgroups were listed as potential subgroups to be assessed if feasible. 
 
Seropositive or seronegative by SARS-CoV-2 nucleocapsid antibody test on or prior to Day 29
 
Receipt of a live non-COVID-19 vaccine within 28 days before or after any study vaccination
 
	These Subgroups will not be defined, and subgroup analyses will not be performed	These analyses will not be performed due to low frequency in one of the two subgroups.
Section 8.4.1 Phase 1/2/3a Substudy	For the seroconversion rate primary immunogenicity objective, the null hypothesis	Following regulatory interactions, a more	More conservative approach added for testing

Statistical Hypothesis	( $H_0^{\text{Immunogenicity}}$ ) is that the lower bound of the 95% CI for ARCT-154 seroconversion rate ( $SC^{154}$ ) is $\leq$ seroconversion rate for placebo ( $SC^{\text{Placebo}}$ ); i.e., $H_0^{\text{Immunogenicity}}$ : lower bound 95% CI for $SC^{154} \leq SC^{\text{Placebo}}$	conservative methodology has been added: 

• <math>H_0^{\text{Immunogenicity}}</math>: lower bound of the 95% CI of <math>(SC^{154} - SC^{\text{Placebo}}) \leq 0\%</math> , versus

• <math>H_1^{\text{Immunogenicity}}</math>: lower bound of the 95% CI of <math>(SC^{154} - SC^{\text{Placebo}}) > 0\%</math>

	
------------------------	---	---	--

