3.1 Phase 1/2/3a Substudy

Immunogenicity data from participants in Phases 1, 2 and 3a will be pooled for analysis up to Day 92. With implementation of protocol version 8.0, participants in Phase 2 and 3a that received ARCT-154 in the initial vaccination series are further randomized to receive a 3rd vaccination of either ARCT-154 or placebo at Day 92 followed by placebo at Day 120 in order to compare immunogenicity after 3 injections of ARCT-154 with that after 2 injections.

Therefore, after Day 92 only data from Phase 2/3a will be pooled and will be displayed separately from participants in Phase 1.

Safety data from participants in Phase 2/3a will be pooled for all time points and will be displayed separately to safety data from Phase 1.

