4.1 Number of Participants

Enrollment of approximately 19,400 participants across all phases of the study is planned, as follows:

- Phase 1: 100 (75 ARCT-154:25 placebo per study group)
- Phase 2: approximately 300 (225 ARCT-154:75 placebo per study group)
- Phase 3a: approximately 600 (450 ARCT-154:150 placebo per study group)
- Phase 3b: approximately 16,000 (8,000 per study group)
- Phase 3c: approximately 2,400 (~1,200 per study group)
 - o The first approximately 1,500 participants will be enrolled into Phase 3c-1, the group that will have blood drawn for immunogenicity assessments. Data from 800 participants in this subgroup will be used to establish the noninferiority of immunogenicity of ARCT-154 vaccine as compared to ChAdOx1
 - o The remaining ~900 participants will form Phase 3c-2

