Phase 1 participants must be <60 years of age. Phase 2, 3a, 3b and 3c participants will include elderly (≥ 60 years) participants as well. Phase 3b and Phase 3c will enrich for participants at higher risk for COVID-19 by attempting to enroll individuals considered at high risk due to their workplace environment or living conditions.

For Phases 2, 3a, 3b and 3c, after a 10-day Screening period, prior to randomization, participants will be stratified by age (< 60 or ≥ 60 years of age) and for participants < 60 years of age by risk of severe COVID-19. Participants will be defined as “at risk” if they are 60 years of age or older OR have medical history described as putting the individual at risk or possibly at risk of severe coronavirus disease 2019 (COVID-19) ([Appendix 5](#)). As the eligibility criteria for Phase 1 exclude participants ≥ 60 years of age or otherwise at risk for severe COVID-19, stratification will not occur for Phase 1.

Participants in all study phases will undergo informed consent and screening procedures prior to enrollment. After enrollment, participants will be randomized to groups. Study vaccines will be given in a supervised medical setting. All participants will be evaluated for reactogenicity (solicited adverse events) and reporting of unsolicited adverse events and concomitant medications through a series of clinic visits and phone calls. Depending on the study phase, blood sampling for immunogenicity and testing for COVID-19 may be performed. See [Appendix 1](#) for an overview of study visits by study phase.

For participants in Phase 1/2/3a/3b, at the Day 92 visit and prior to receipt of further study vaccine, participants will be evaluated by the Investigator according to Further Study Vaccine eligibility criteria (Section [5.1.5](#)). Any participant who does not meet these criteria will not receive further vaccinations with study vaccine and will be asked to continue in the study through Final Visit (Day 394).

For participants that receive further doses of Study Vaccine at Day 92 and Day 120, this will occur in a blinded fashion in that participants and blinded site and Sponsor personnel will remain blinded to treatment assignment until End of Study (EOS).

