12. Has received treatment with immunosuppressive therapy, including cytotoxic agents or systemic corticosteroids, eg, for cancer or an autoimmune disease, within 6 months prior to Screening, or planned receipt throughout the study. If systemic corticosteroids have been administered short term (<14 days) for treatment of an acute illness, participants should not be enrolled into the study until corticosteroid therapy has been discontinued for at least 28 days prior to first study vaccine administration. Inhaled/nebulized, intra-articular, intrabursal, or topical (skin or eyes) corticosteroids are permitted.
13. Has received systemic immunoglobulins or blood products within 3 months prior to first study vaccine administration or plans to receive such products during the study.

Other Exclusions

14. Demonstrated inability to comply with the study procedures.
15. Investigator site staff members, employees of the Sponsor or the CRO directly involved in the conduct of the study, or site staff members otherwise supervised by the investigator, or immediate family members of any of the previously mentioned individuals.

Additional Exclusion Criteria for Phase 1 Participants Only

16. Individuals \geq 60 years of age.
17. Individuals with clinically significant abnormalities in medical history or physical examination, including but not limited to, the following:
 - a) Respiratory disease (e.g., chronic obstructive pulmonary disease [COPD], asthma) requiring daily medications or oxygen currently or any treatment of respiratory disease exacerbations (e.g., COPD or asthma exacerbation) warranting hospitalization or an emergency room visit or supplemental oxygen in the last 5 years.
 - b) Significant cardiovascular disease (e.g., congestive heart failure, cardiomyopathy, ischemic heart disease) or history of myocarditis or pericarditis as an adult.
 - c) Neurological or neurodevelopmental conditions (e.g., migraines, epilepsy, stroke, seizures in the last 3 years, encephalopathy, focal neurologic deficits, Guillain-Barré syndrome, encephalomyelitis or transverse myelitis).
 - d) Significant hematologic abnormalities (e.g., sickle cell disease, beta thalassemia, coagulation disorders).
 - e) Major surgery within the past 6 months.
 - f) Individuals with a history of chronic liver disease.
18. Individuals with the following abnormal Screening laboratory results:

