## 2 STUDY DESIGN

### 2.1 Introduction to Study Design

This is a Phase 1/2/3, randomized, placebo- and active-controlled, observer-blind study designed to evaluate the safety, immunogenicity and efficacy of ARCT-154 in adult participants to be enrolled in Vietnam. The full details of the study design are available in protocol Section 4.4 and illustrated in protocol's Figure 1.

The study design included 5 different enrollment phases:

- Phase 1: healthy participants  $\geq 18$  to  $<60$  years of age, enrolled as a sentinel cohort evaluating the safety and immunogenicity of ARCT-154 versus placebo (3:1 randomization)
- Phase 2 and 3a: healthy and “at-risk” participants  $\geq 18$  years of age, respectively, evaluating safety and immunogenicity of ARCT-154 versus placebo (3:1 randomization)
- Phase 3b: healthy and “at-risk” participants  $\geq 18$  years of age, respectively, evaluating safety and efficacy of ARCT-154 versus placebo (1:1 randomization)
- Phase 3c: healthy and “at-risk” participants  $\geq 18$  years of age, respectively, evaluating safety and immunogenicity of ARCT-154 versus authorized AstraZeneca COVID-19 vaccine (1:1 randomization)

An important element of the study design is that there is a “Switchover” or “Re-randomization” stage at Day 92 in Phase 1, 2, 3a, and 3b. At that milestone, participants who were originally assigned to receive placebo in Phases 1, 2, 3a and 3b will receive two subsequent doses of ARCT-154 on Day 92 and Day 120. Participants in Phase 1 and Phase 3b who were originally assigned to receive ARCT-154 will receive two subsequent doses of placebo on Day 92 and Day 120. Participants in Phase 2 and Phase 3a who were originally assigned to ARCT-154 will be re-randomized at 3:1 ratio either to receive third dose of ARCT-154 on Day 92 and dose of placebo on Day 120 or to receive two subsequent doses of placebo on Day 92 and Day 120. Phase 3c participants will not switchover treatments.

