**Table 8 Overview of Safety Endpoints**

	Description	Analysis Set and timepoint
--	-------------	----------------------------

Solicited AEs	Occurrence of solicited AEs within 7 days after each study vaccine administration	Phase 1/2/3a RAS: after Day 1 and Day 29 doses Phase 3b RAS: after Day 1 and Day 29 doses Phase 2/3a RAS: After Day 92 Phase 3c RAS: after Day 1 and Day 29 doses Pooled RAS: after Day 1 and Day 29 doses
	Occurrence of solicited AEs within 30 minutes after each study vaccine administration. Occurrence of solicited AEs by grade	Phase 1/2/3a RAS: after Day 1 and Day 29 doses Phase 3b RAS: after Day 1 and Day 29 doses Phase 2/3a RAS: After Day 92 DosePhase 3c RAS: after Day 1 and Day 29 doses Pooled RAS: after Day 1 and Day 29 doses
Unsolicited AEs	Occurrence of unsolicited AEs up to 28 days after each study vaccine administration up to Day 92 (dose 1, dose 2)	Phase 1/2/3a SAS Phase 3b SAS Phase 3c SAS Pooled SAS
	Occurrence of unsolicited AEs up to 28 days after each study vaccine administration after switchover/receipt of further study vaccine	Phase 1/2/3a SAS Phase 3b SAS Pooled SAS
SAEs, MAAEs, AEs leading to discontinuation of treatment, AEs leading to discontinuation of Study	Occurrence of AEs leading to discontinuation, MAAEs, or SAEs up to Day 92 or Switchover/Further Study Vaccine or receipt of non-study COVID-19 vaccine	Phase 1/2/3a SAS Phase 3b SAS Phase 3c SAS Pooled SAS

	Occurrence of AEs leading to discontinuation, MAAEs, or SAEs in other time intervals	Phase 1/2/3a SAS Phase 3b SAS Phase 3c SAS Pooled SAS
--	--	--

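### The SAP pools Phase 1 with Phase 2/3a for safety on an incorrect eligibility premise, so the post-Day 92 unsolicited AE and SAE tables no longer show the re-randomised third-dose comparison

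*SAP*

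**What the plan says.** **Protocol.** Section 3.1 pools Phase 2/3a safety data at all time points and says they "will be displayed separately to safety data from Phase 1". Section 8.2 defines a Phase 2/3a safety set and limits the Phase 1/2/3a safety set to Day 92.

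**SAP.** Section 7.1 replaces this with displays mostly on Phase 1/2/3a, and gives as its reason that they come "with same inclusion and exclusion criteria across Phase 1/2/3a, so not relevant to display safety from a smaller phase 1 set separately". The Phase 1/2/3a safety set is kept in Section 4.1 without the Day 92 limit, and no Phase 2/3a safety set is listed there.

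On the merged set, Table 8 plans "Occurrence of unsolicited AEs up to 28 days after each study vaccine administration after switchover/receipt of further study vaccine". Section 6.6.1.2 asks for tables after Dose 3 and after Dose 4. Section 6.6.1.3 adds SAEs, MAAEs and discontinuations from switchover to end of study.

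**Eligibility.** Protocol 4.4 states that "Phase 1 participants must be <60 years of age". Section 5.1.2 has a block headed "Additional Exclusion Criteria for Phase 1 Participants Only", covering age, screening laboratory results and "Individuals with clinically significant abnormalities in medical history or physical examination, including but not limited to, the following".

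**Day 92.** SAP 2.1 says participants in "Phase 1 and Phase 3b who were originally assigned to receive ARCT-154 will receive two subsequent doses of placebo". Phase 2/3a participants who began on ARCT-154 are instead re-randomised 3:1 to a third dose or placebo.

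**The concern.** Among participants who began on ARCT-154, only those in Phase 2/3a were randomised between a third dose and placebo. That makes the Phase 2/3a contrast the one fair control for adverse events after a third dose. The planned post-switchover header (SAP 5.3.1) has a single placebo column for initial ARCT-154 recipients, and Phase 1 participants fall into it by design rather than by chance. The third-dose column beside it contains no Phase 1 participants.

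Eligibility is not the only difference between the cohorts:

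- Phase 2/3a enrolment began only after review of Phase 1 data through Day 36 (Protocol 4.4), so calendar time differs.
- After Day 92 only Phase 2/3a completes a diary (Protocol Appendix 1). A post-injection symptom that is solicited in Phase 2/3a could be recorded in Phase 1 only as an unsolicited AE.
- The minimum post-dose observation time and the Day 92 visit window also differ by phase (Protocol Appendix 1).

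A reader of these tables would naturally take the two adjacent columns as a randomised comparison of third dose against placebo. For unsolicited AEs, SAEs, MAAEs and discontinuations they would not be one.

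**Working it through.** **1. Is the premise true?** No. Protocol 5.1.2 confines criteria 16 to 18 to Phase 1, and Protocol 4.4 sets the age limit for Phase 1 only. SAP 2.1 itself describes Phase 1 as healthy and under 60, and Phase 2/3a as healthy and at-risk participants aged 18 or over.

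**2. The plan's own safety-size figure.** SAP 6.1 and Protocol 8.5.1 use p = 1 − (1 − R)^N.
- N = 75 + 225 + 450 = 750 and R = 1.0% give 1 − 0.99^750 = 0.9995, which agrees with the stated >99%.
- Phase 2/3a alone: N = 675 gives 1 − 0.99^675 = 0.9989, still above 99%. Showing Phase 1 separately does not forfeit the stated target.

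**3. Make-up of the columns after Day 92.** Inputs from Protocol 4.1: "Phase 1: 100 (75 ARCT-154:25 placebo per study group"), with ARCT-154 arms of 225 in Phase 2 and 450 in Phase 3a. Planned numbers, no attrition.
- Phase 2/3a ARCT-154 recipients: 225 + 450 = 675.
- Third dose: 675 × 3/4 = 506.25, about 506.
- Re-randomised to placebo: 675 × 1/4 = 168.75, about 169.
- Merged placebo column: 168.75 + 75 = 243.75, about 244.
- Share not re-randomised: 75 / 243.75 = 30.8%.
- Third dose to placebo: 506.25 / 168.75 = 3.0 as randomised; 506.25 / 243.75 = 2.08 as displayed.

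**4. Sensitivity to attrition.** The documents give no retention by phase. Assume between 50% and 100% of either group reaches Dose 3.
- Phase 1 at 50%, Phase 2/3a at 100%: 37.5 / (37.5 + 168.75) = 18%.
- Phase 1 at 100%, Phase 2/3a at 50%: 75 / (75 + 84.375) = 47%.

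**5. Pooled tables after Doses 3 and 4.** Phase 3b adds up to about 8,000 ARCT-154 recipients switched to placebo, so the re-randomised share is 168.75 / (8,000 + 243.75) = 2.0%. SAP 4.1 limits the Pooled safety set to Day 92 except for unsolicited events, and SAP 6.6.1.3 gives it only the interval ending at Day 92 or switchover. The Pooled problem therefore lies in the 28-day unsolicited AE tables. (Table 8 does name the Pooled set in its row for other intervals, but 6.6.1.3 specifies none.)

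**6. Illustration of the distortion.** AE rates by phase are not in the documents, so these are assumptions. Let r be the Phase 1 risk divided by the Phase 2/3a risk, and suppose the third dose has no effect. The apparent risk ratio is 243.75 / (168.75 + 75r).

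| r | Apparent risk ratio | Shift in risk difference if the Phase 2/3a rate is 10% |
|---|---|---|
| 0.25 | 1.30 | +2.3 points |
| 0.50 | 1.18 | +1.5 points |
| 0.75 | 1.08 | +0.8 points |
| 1.25 | 0.93 | −0.8 points |

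**7. Consistency within the SAP.** Section 7.2 still says safety will rest on a Phase 2/3a safety set as well as the Phase 1/2/3a set. Sections 5.3 and 5.3.1 keep separate Phase 1 and Phase 2/3a reporting. Section 4.1, Table 8 and Sections 6.6.1.2 and 6.6.1.3 list no such set. For immunogenicity, Section 6.5 pools only Phase 2/3a after Day 92, and Table 8 places solicited AEs after Dose 3 on the Phase 2/3a reactogenicity set. The SAP thus follows the right principle everywhere except the remaining safety tables.

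**The case against.** The strongest reply is that little depends on these tables. The re-randomisation was introduced to compare immunogenicity (Protocol 3.1). The primary Phase 1/2/3a safety analysis is at Day 92 and later safety analyses are exploratory (Protocol 8.9.1). There is no safety hypothesis test (SAP 6.2.3), and confidence intervals for adverse events have been dropped (SAP 7.2). All of this stands and limits the consequence to a misleading display; no type I error is at issue. Yet Protocol 8.9.1 also foresees an evaluation of safety after the third dose, so the display will be read.

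It can also be said that the protocol is mixed. Its Table 2 allows exploratory analyses on the Phase 1/2/3a safety set, and its Table 18 summarises events from Day 92 to Day 394 for Phase 1/2/3a. That is fair, but neither passage withdraws the separate display, and Section 8.2 limits the merged set to Day 92.

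The SAP says only that safety analyses will mostly be merged, and Section 5.3.1 has a header for combined data from before and after switchover with a column for those not re-randomised. The header for data after switchover has no such column, and no adverse event table is assigned to a Phase 2/3a safety set.

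A reader might infer that the whole third-dose safety comparison is compromised. It is not: solicited AEs after Dose 3 use Phase 2/3a only. Nor were Phase 1 participants unrandomised: they were allocated 3:1 on Day 1, and were only not re-randomised at Day 92. Before Day 92 all three phases share the 3:1 allocation, so pooling then does not unbalance the arms by phase.

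**Conclusion.** Wrong as written. The reason given in SAP 7.1 is contradicted by the protocol and by SAP 2.1. Following the SAP puts about 75 fixed-switchover Phase 1 participants with about 169 re-randomised ones: 31% of the comparator, or 18% to 47% under the assumed retention range. For unsolicited AEs, SAEs, MAAEs and discontinuations after Day 92, the Phase 1/2/3a contrast of third dose with placebo is therefore not the randomised one. In the Pooled set the same applies to the 28-day unsolicited AE tables only, where about 2% of the column is re-randomised.

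It would be tempting to add that the comparator is healthier and so makes the third dose look worse. The documents do not support a direction. They give no event rates or risk mix by phase, and the absence of a diary in Phase 1 after Day 92 could raise its unsolicited count. The figures rest on planned arm sizes and, in the illustration, on assumed rates.

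**What to change.** - Define the Phase 2/3a safety set in SAP 4.1.
- Use it in Table 8 and Sections 6.6.1.2 and 6.6.1.3 for every post-Day 92 AE, SAE, MAAE and discontinuation table that sets the third dose beside placebo.
- Show Phase 1 post-switchover data in separate tables. Phase 3b already has its own.
- Do not present the Pooled Dose 3 and Dose 4 columns as a comparison of third dose with placebo.
- Correct the eligibility rationale in SAP 7.1, including the immunogenicity row that repeats it, and bring Sections 5.3, 5.3.1 and 7.2 into line with Section 4.1.

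The cost is a subset filter on tables already planned, plus a small set of Phase 1 tables. No new data are needed, and the stated detection target is still met with 675.
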